To assess peripheral effects, we used pain report to 5 minute exposure to a 45°C stimulus, since our studies in rodents shows that prolonged noxious heat sensitizes and increases activity the fast conducting pain fibers which are sensitive to oxytocin [9]. **Figure 1B** shows the modeled plasma oxytocin concentrations in the 11 subjects in **Figure 1A** and pain report to a 5 min noxious heat exposure. The data were nicely fit to a PK/PD model yielding parameters of 25 min to peak effect, an EC50 of 10 pg/ml, and steepness of concentration response (γ) of 1 (green dashed lines). The goal of this PK study was to determine oxytocin PK and to explore a potential effect on pain from skin heating. Under IRB00066136 we examined the time course of analgesia to skin heating by slower infusion of IV oxytocin (0.47 μ g/min for 30 min for a total dose 14 μ g) in 10 volunteers. There were no adverse events with this dosing regimen, and the PK/PD model from the first study accurately predicted the time course of onset of analgesia during infusion and maintenance of analgesia after the infusion was stopped (**Figure 1C**).

The primary objective of the current IRB application is to determine the dose response of IV oxytocin for analgesia to experimental heat pain at the time of anticipated maximum effect.

Figure 1. A) plasma oxytocin concentrations with LC/MS (red/black lines) compared to plasma by RIA (blue lines. B) modeled plasma oxytocin concentrations (blue line) and observed (circles) and modeled (green dash) pain scores after 10 min infusion of 17 μ g oxytocin. C) as in B) but after 30 min infusion of 14 μ g oxytocin

The proposed study design will advance the preliminary data by use of a placebo controlled, partially randomized dose response with each subject being tested on two separate study days and receiving on each study day two 10-min IV infusions of study drug separated by one hour (**Figure 2A**). As shown in this figure, the preliminary PK/PD model predicts that infusions of 0.3, 1.3, and 7 μ g in these paradigms will result in analgesic effects of approximately 20%, 50%, and 85% of the maximum. The PK/PD model further predicts a relatively stable drug effect with this infusion paradigm from 10 to 50 min after the end of the infusion.

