These infusion times and oxytocin dosages were also chosen to minimize adverse events observed in our previous studies. In the original PK study (IRB00056413) adverse events were observed in 5 of 8 individuals who received a 10 min infusion of 17 μ g oxytocin. Adverse events were facial flushing and sensation of hear pounding despite no change in heart rate or blood pressure, similar to adverse events commonly observed with rapid IV infusion of oxytocin at cesarean delivery to rapidly contract the uterus after delivery of the fetus. Adverse events were not observed below plasma oxytocin concentrations of 400 pg/ml, and in the second study (IRB00066136) in which we infused oxytocin to a modeled concentration of 400 pg/ml, no adverse events were observed. As shown in **Figure 2B**, plasma oxytocin concentrations with the largest oxytocin infusion are modeled to not exceed 400 pg/ml, and we therefore anticipate few if any of these adverse events.

Objectives

Main objective Determine dose-response of IV oxytocin infusions to reduce pain from an experimental heat stimulus

Additional Objectives

1. Test for effects of subject sex or age on oxytocin effect
2. Refine the PK/PD model for oxytocin analgesic action based on time course of observations

Methods and Measures

Equal numbers of adult men and women will be recruited. Sample size will be divided into 3 groups; young (18-39-year-old) middle (40 – 59-year-old) and older (60 – 75-year-old). We anticipate that approximately 20% of subjects will be in the elderly group, 35% will be in the middle age group, and 45% will be in the young group.

Subjects will report to the Pain Clinical Research Unit (CRU) or the CTSI CRU for three visits

[figure not shown]

Figure 2. **A)** predicted drug effect over time after two 10-min IV infusions (Inf. 1 and 2) separated by one hour on 2 study days, one with 0.3, then 7 μ g and the other with 0, then 1.3 μ g. Time of heat pain testing shown in red squares. **B)** predicted oxytocin plasma concentrations following the infusions in **A)**

We will abandon an individual participant's study and schedule another participant should the participant report minimal pain to the heat stimulus on the training visit day or should we be unable to successfully place the intravenous catheter.

STUDY DESIGN

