This is a blinded, randomized, controlled study of IV infusion of placebo and 3 doses of oxytocin. In this study, healthy individuals will come to the Piedmont Plaza 2 Pain Clinical Research unit (CRU) or the CTSI CRU for a training visit and then to the CTSI CRU for two other study days, separated by at least 72 hr. During the training day they will report pain on a 0 (no pain) to 10 (worst imaginable pain) scale each minute during a 5 min heating of the skin of the lateral calf to a temperature (45°C) using an FDA approved, commercially available device (Medoc, TSA II). If pain score is less than 2 at the end of this stimulus, the test will be repeated with the probe set to 46°C. If pain score is less than 2 on that occasion, the test will be repeated with the probe set to 47°C. If pain score is less than 2 on that occasion the individual will not go on to further study and will be reimbursed for the training day only. On the other two visits, subjects will receive on one visit IV saline followed in one hour by IV oxytocin, 1.3 µg and on the other visit they will receive IV oxytocin, 0.3 µg followed in one hour by IV oxytocin, 7 µg. Infusions will be given over 10 minutes. The order of these two dosing regimens will be randomized and double blind, with solutions released from the research pharmacy. As a result, each subject will receive oxytocin doses of 0, 0.3, 1.3, and 7 µg in this double blind design. Pain report each minute and at the end of a 5-min heating will be recorded before the first infusion and then with the 5-min heat test ending at 15, 30, and 45 min after the ending of the infusion. The probe temperature used for heating will be that determined during the training day. Immediately after the 60 min pain report the second infusion will be given and pain intensity at the end of 5-min of heating recorded at 15, 30, and 45 min thereafter. The study will then end.

Phase II trials

Setting

The training visit will occur at either the Pain CRU at Piedmont Plaza 2 or the CTSI CRU. Drug study visits will occur on the main campus at CTSI CRU.

Subjects selection criteria

The study will enroll healthy subjects.

Inclusion Criteria

1. Male or female ≥ 18 and < 75 years of age, Body Mass Index (BMI) <40 .
2. Generally in good health as determined by the Principal Investigator based on prior medical history, American Society of Anesthesiologists physical status 1, 2, or 3
3. Fully vaccinated against COVID-19

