On the second visit, the participant will report to the CTSI CRU. Baseline vital signs (BP, HR, Resp, POX) will be obtained for a baseline measurement, a catheter inserted into a peripheral vein in the upper extremity and pain report to 5 min heating of skin on the calf at the temperature determined in Visit 1 will be recorded. Subjects will then receive two 10 min infusion of study drug, with infusions separated by 60 min and 5 min heat pain testing performed with each 5 min test ending at 15, 30, and 45 min after the end of each infusion. Subjects will be randomized to receive either 1) IV infusion of saline followed by oxytocin, 1.3 µg or 2) IV infusion of oxytocin 0.3 µg followed by oxytocin 7 µg. Which of these regimens is administered on study visit 2 will be randomized and double blind, with study drugs provided by the research pharmacy. The intravenous catheter will be removed after all data collection and the subject discharged from the CRU. The duration for study visit 2 will be approximately 4 hours.

Study Visit 3

On the third visit, the participant will report to the CRU and all procedures performed as in study visit 2. The pair of IV infusions will be the alternate to that used in study visit 2. The duration for study visit 3 will be approximately 4 hours.

Safety and Monitoring:

Assessment of Side Effects: Significant side effects are defined as changes > 30% from baseline in the mean arterial pressure, HR, or oxyhemoglobin pulse oximetry < 90. Any unexpected or serious side effects will be reported to the IRB within 24 hrs. Peripheral oxyhemoglobin saturation, BP and HR will be measured non-invasively before and 15, 30, and 60 min after each IV infusion. If either BP or HR change by > 30%, or oxyhemoglobin saturation decreases to less than 90, and require treatment, these vital signs will be repeated at 5-minute intervals until vital signs are stabilized.

Treatment of Side Effects: Mean blood pressure elevations greater than 30% of baseline will be treated with labetalol 5-15 mg IV incrementally until BP elevation is less than 30% elevated. Reductions in mean BP > 30% of baseline will be treated with incremental ephedrine 5-20 mg, IV. Heart rate (HR) reductions or elevations > 30% of baseline will be treated with incremental glycopyrrolate 0.2 mg IV or propranolol 0.2 mg IV, respectively. Peripheral oxyhemoglobin

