Covariate effects deemed significant by likelihood ratio test will be validated using jackknife cross-validation [10]. Jackknife cross-validation provides an estimate of the utility of the covariate to inform the pharmacodynamics in a future individual, rather than merely characterize the pharmacodynamics in the individuals from which the model was derived. The jackknife cross-validation divides the data into N subsets. Each subset leaves out a single individual. The parameters of the model are re-estimated for each subset with and without the covariate being validated. The inaccuracy (mean $((|measured - predicted|) / predicted)$), of the model with and without the covariate is measured in the excluded individual. The covariate is only being included in the final model if the improvement in model accuracy in the N iterations is significantly greater than 0. Jackknife cross-validation helps compensate for NONMEM's ability to identify very small covariate effects that do not meaningfully contribute to accuracy in future patients.

Expected outcomes. Based on pain ratings and an estimate of the PK/PD model from preliminary data (Fig 1), we anticipate that the maximum oxytocin effect is a 50-60% reduction in pain rating from the 5 min heat stimulus. We anticipate that the oxytocin dose range will demonstrate a sigmoidal dose-response with a peak within 10 min after the end of infusion and an ED80 of ~ 5 μ g. In a separate simulation of 7 μ g oxytocin without a prior injection of 0.3 μ g, the peak effect was within 1% of the same value, supporting this stepped dosing study design. The expected peak plasma oxytocin concentration after the 7 μ g infusion following the 0.3 μ g infusion is 400 pg/ml, below that which produced subjective symptoms in previous studies.

Human Subjects Protection

Subject Recruitment Methods

Healthy subjects will be recruited from our current database of volunteers BG05-468, word of mouth and Be Involved website; The research nurses; [name] and [name], LPN will conduct the recruitment of study subjects.

Potential subjects from the database will be contacted via phone or email, per their request. Potential subjects from the Be Involved website will be contacted according to the information they provide.

Informed Consent

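### No blood pressure, heart rate or saturation reading is scheduled during or at the end of the 10-minute infusion, when plasma oxytocin is highest

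*Combined protocol and SAP*

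**What the plan says.** Safety and Monitoring schedules saturation, blood pressure and heart rate "measured non-invasively before and 15, 30, and 60 min after each IV infusion". The same section defines a significant side effect as a change of more than 30% in mean arterial pressure or heart rate, or a saturation below 90, and links drug treatment or oxygen to those limits. If a value crosses a limit and needs treatment, "these vital signs will be repeated at 5-minute intervals until vital signs are stabilized". No other section adds a reading, or continuous monitoring, during or at the end of an infusion.

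Infusions run for 10 min (STUDY DESIGN) at a constant rate (table comparing this study with IRB00066130). On exposure, the rationale says that "plasma oxytocin concentrations with the largest oxytocin infusion are modeled to not exceed 400 pg/ml", and Expected outcomes says that the peak after the 7 µg "infusion is 400 pg/ml, below that which produced subjective symptoms in previous studies". The rationale also reports that no adverse events were seen below 400 pg/ml.

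Two earlier studies bear on risk. At 17 µg over 10 min, 5 of 8 volunteers had flushing or a pounding sensation "despite no change in heart rate or blood pressure". In the slower study, "in which we infused oxytocin to a modeled concentration of 400 pg/ml, no adverse events were observed"; it infused 14 µg over 30 min in 10 volunteers.

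**The concern.** The schedule measures vital signs on both sides of the point of highest exposure, but not at it. The limits of 30% and 90 can act only on values that someone records. A brief, symptomless change near the end of infusion could therefore pass without being recorded, treated or reported, unless staff happen to take an unscheduled reading. The 5-minute repeats do not close the gap, because they start only after an abnormal value has been found and needs treatment.

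The issue is mainly the 7 µg infusion, the only one with a modelled peak near 400 pg/ml. The population adds some weight: eligibility allows "American Society of Anesthesiologists physical status 1, 2, or 3", treated hypertension and ages up to 75. What is at stake is the completeness of safety data and the chance to act on it. The pain analysis is untouched.

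**Working it through.** **1. When the plasma peak occurs.** With a constant-rate intravenous infusion, plasma concentration rises until the infusion stops and then falls. As a check, 300 random two-compartment parameter sets were simulated with a 10-min infusion. All 300 peaked at the end of infusion. The peak that Expected outcomes places within 10 min after the infusion is that of the analgesic dose-response, which is a different quantity.

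**2. Length of the unmeasured interval.** Inputs: 10-min infusion; first later reading at 15 min.
- Timed from the end: 10 + 15 = 25 min at least, since the pre-infusion reading may be earlier than the start.
- Timed from the start: about 15 min, with the reading 15 − 10 = 5 min after the end.

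Study Visit 2 times the heat tests explicitly from the end of infusion. The vital-sign sentence has no such anchor. STUDY DESIGN places the second infusion right after the 60-min assessment, so the 60-min reading from the first infusion is not a reading at the peak of the second.

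**3. Which infusions matter.** Scaling the modelled 400 pg/ml at 7 µg (linear kinetics assumed):
- saline: 0
- 0.3 µg: 400 × 0.3/7 = 17 pg/ml
- 1.3 µg: 400 × 1.3/7 = 74 pg/ml
- earlier 17 µg over 10 min: 400 × 17/7 = 971, about 970 pg/ml; dose ratio 17/7 = 2.4

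**4. How much drug remains at the first reading.** The documents give no half-life, so this is an assumed range with single-exponential decline. The fraction of peak left t minutes after the end is 2^(−t/h).

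| Half-life h | 15 min after end | 5 min after end |
|---|---|---|
| 3 min | 0.031 (12.5 of 400 pg/ml) | 0.315 (126) |
| 10 min | 0.354 (141) | 0.707 (283) |
| 20 min | 0.595 (238) | 0.841 (336) |

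One illustrative value comes from taking both modelled 400 pg/ml figures at face value in a one-compartment model: (14/30)(1 − e^(−30k)) = (7/10)(1 − e^(−10k)). With x = e^(−10k) this reduces to x² + x = 0.5, so x = 0.366, k = 0.1005 per min and the half-life is 6.9 min. About 22% of peak (89 pg/ml) would remain at 15 min after the end, and about 60% (242 pg/ml) at 5 min. The protocol's own model has two compartments, so this is only a guide. All these figures describe plasma level, not haemodynamic effect, and the conclusion does not depend on them.

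**5. What the earlier data can exclude.** With no events in n people, the one-sided 95% upper bound on the rate is 1 − 0.05^(1/n).
- Slower study, n = 10: 26%.
- 17 µg over 10 min, n = 8: 31%. If the remark about heart rate and pressure covers only the five with symptoms, 1 − 0.05^(1/5) = 45%.

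These bounds show how little small samples rule out. They are not expected rates.

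**The case against.** The best case for the plan is that the only haemodynamic evidence in the documents points away from a problem. The 17 µg infusion had the same duration and 2.4 times the top dose here, yet symptoms came without a change in heart rate or blood pressure. Doses and infusion times were then chosen to lower exposure further, and the slower infusion to a modelled 400 pg/ml was free of adverse events. Eligibility requires general good health and controlled blood pressure. It excludes anyone the investigator judges to be at increased risk, certain arrhythmias, and users of several blood-pressure drugs, including the listed diuretics, enalapril and ramipril. Infusions take place in a clinical research unit with intravenous access and a written treatment plan, and volunteers are contacted daily for a week. Nothing in the documents shows that any pressure effect would follow plasma level; for analgesia they describe a delay.

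Most of this stands, and it keeps the point small. It does not remove the gap. The documents do not say when heart rate and pressure were read in the 17 µg study. The slower study ran at about 0.47 µg/min against 7/10 = 0.7 µg/min here. The modelled peak equals the level below which no adverse events were seen, so no margin is stated, and this study takes no blood samples to check it. Follow-up calls would pick up symptoms, but not a silent transient change.

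**Conclusion.** The point holds as a minor one. No vital sign is scheduled at peak exposure. The interval without a scheduled reading is at least 25 min or about 15 min, depending on an anchor that the text leaves open. This rests on the constant-rate infusion and on the absence of any other scheduled reading.

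A reader might infer more than this. One inference is that participants face a material haemodynamic risk, or that events will be missed in some estimable number. The documents give no event rate, and their evidence suggests a low yield. Another is that 25 min is the definite gap; that is true only if the 15 minutes count from the end. A third is that the share of drug remaining at the first reading measures harm. It rests on an assumed half-life and concerns plasma level alone. Nor does the schedule show that participants go unobserved, since staff may take unscheduled readings.

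**What to change.** In Safety and Monitoring, add one reading of blood pressure, heart rate and saturation at the end of each infusion, keep the 15, 30 and 60 min readings, and state that these are timed from the end of infusion. Apply the added reading to all four infusions so that the schedule does not reveal the dose.

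The cost is a sentence of protocol text and four non-invasive readings per subject (4 × 24 = 96 in all), with low expected yield. The first heat test runs from 10 to 15 min after the end of infusion, so the added reading does not clash with pain testing. It is also taken before the post-infusion heat tests, whereas 15 and 30 min readings timed from the end coincide with the close of a painful heat stimulus that could itself shift heart rate or pressure.

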desaturation (< 90) will be treated with supplemental oxygen, nasal cannula, face mask, or non-rebreathing mask depending upon the degree desaturation and the response to therapy.

Outcome Measure(s)

Primary Outcome Measure

Name: Verbal pain score (0-10) at the end of 5 min of skin heating

Type: Primary

Time Frame: For 45 minutes after the end of each study drug infusion

Description: Pain scores are measured each minute during 5 min heating of the skin of the calf

Analytical Plan

The primary analysis will use NONMEM to create a dose response at the time of peak oxytocin effect on pain at the end of a 5 min noxious heat stimulus. To do so, pain scores over time will first be modeled using NONMEM with derived parameters of maximum effect (Emax), predicted concentrations from the PK/PD model to produce a 50% and 90% maximum drug effect (C50 and C90, respectively), the steepness of the dose response curve (γ), and the time to peak effect. Inter-subject variability (e.g., biological variability) will evaluate additive, proportional, and exponential models. Residual intrasubject variability (e.g., noise) will typically require an additive and multiplicative error model. The influence of covariates (e.g., age, sex, weight) on model parameters will be analyzed by serial inclusion / exclusion, with significance determined by the likelihood ratio test ($p < 0.01$ if the decrease in $-2 \log$ likelihood exceeds 6.6 ($\chi^2_{0.99}$, $df = 1$)). Parameters will be estimated using first-order conditional estimate with η - ε interaction.

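### The Analytical Plan specifies no oxytocin-versus-saline comparison, placebo-response term or criterion for a drug effect, and does not say how saline and pre-infusion scores enter the model

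*Combined protocol and SAP*

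**What the plan says.** The Rationale section says the design will advance the preliminary data "by use of a placebo controlled, partially randomized dose response". The Study Design section opens: "This is a blinded, randomized, controlled study of IV infusion of placebo and 3 doses of oxytocin". It adds that "each subject will receive oxytocin doses of 0, 0.3, 1.3, and 7" µg, so saline is dose level 0 in every subject. One of the two daily regimens is "1) IV infusion of saline followed by oxytocin, 1.3" µg (Study Visit 2); the other is 0.3 µg followed by 7 µg. Only the order of the regimens across visits is randomised. Saline and 0.3 µg are therefore always first infusions, and 1.3 and 7 µg always second.

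Pain "will be recorded before the first infusion and then with the 5-min heat test ending at 15, 30, and 45 min" after the infusion ends, and the three tests are repeated after the second infusion. The Outcome Measures section limits the primary outcome's time frame to the 45 minutes following each infusion.

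Under the Analytical Plan, scores are "modeled using NONMEM with derived parameters of maximum effect (Emax), predicted concentrations from the PK/PD model" giving 50% and 90% of maximum effect (C50 and C90), steepness (gamma) and time to peak. Variability models, covariate selection and jackknife validation follow. Neither saline nor placebo is mentioned in that section. The likelihood ratio threshold of 6.6 (p < 0.01) is set for covariates only.

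**The concern.** Predicted concentration is zero both before any infusion and after saline. A model whose effect terms all depend on concentration predicts the same pain for both, unless it has another term or the pre-infusion scores are left out. If an infusion lowers reported pain through expectation or attention, saline scores fall below pre-infusion scores. A baseline fitted to both then lies above the saline level, and each oxytocin dose is credited with the gap.

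The main objective is the dose-response of oxytocin. An unmodelled common response could raise the low-dose effect and distort ED50/C50, gamma and Emax. It could even produce an apparent effect of an inactive drug. With no stated criterion for a drug effect, the plan also does not say what result would show that oxytocin works better than saline.

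**Working it through.** **Inputs from the protocol.** Expected maximum effect 50-60% (55% used). Predicted effects of about 20%, 50% and 85% of maximum at 0.3, 1.3 and 7 µg. ED80 about 5 µg. Gamma 1 in the preliminary model. Each subject has 2 pre-infusion tests and 3 tests after each of 4 infusions, 14 in all.

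**Assumption.** The documents give no placebo-response size. Write p for a proportional response that multiplies every post-infusion score, saline included, by (1 − p); p = 10% and 20% are shown. The effect is taken as flat over the three tests.

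**Step 1: the plan's own curve.** Share of maximum = D/(D + 1.3): 0.3/1.6 = 18.75%, 1.3/2.6 = 50.0%, 7/8.3 = 84.3%. ED80 = 4 × 1.3 = 5.2 µg. These agree with the protocol. At Emax 55% the true effects are 10.3%, 27.5% and 46.4%.

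**Step 2: pre-infusion and saline scores share one baseline.** With pre-infusion pain set to 1 and p = 10%, the mean of the five zero-drug records is (2 × 1 + 3 × 0.9)/5 = 0.94. With gamma free, the three dose means are fitted exactly, so this is the fitted baseline. At 0.3 µg the expected score is 0.9 × (1 − 0.103) = 0.807, and the fitted effect is 1 − 0.807/0.94 = 14.1%. The baseline stands 0.04 above saline, so about 40% of the common response is credited to drug. With gamma fixed at 1, least squares gives 12.8% and an ED50 of 0.99 µg. With gamma free, gamma is 0.83 and Emax 61%.

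**Step 3: effect measured from pre-infusion pain.** At 0.3 µg, 1 − 0.807 = 19.3%. The whole common response is counted as drug effect.

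**Step 4: only post-infusion scores fitted.** The zero-dose level is saline at 0.9. At 0.3 µg, 1 − 0.807/0.9 = 10.3%, so there is no bias.

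Fitted effects at p = 10%:

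| Handling of zero-dose records | 0.3 µg | 1.3 µg | 7 µg |
|---|---|---|---|
| True effect | 10.3% | 27.5% | 46.4% |
| Shared baseline, gamma fixed at 1 | 12.8% | 31.3% | 48.2% |
| Shared baseline, gamma free | 14.1% | 30.6% | 48.7% |
| From pre-infusion pain, gamma free | 19.3% | 34.8% | 51.7% |
| Post-infusion scores only | 10.3% | 27.5% | 46.4% |
| Shared baseline plus placebo term | 10.3% | 27.5% | 46.4% |

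At p = 20% with a shared baseline, the 0.3 µg effect is fitted as 16.4% (gamma fixed) or 18.5% (gamma free). With gamma free the check is a baseline of (2 + 3 × 0.8)/5 = 0.88 and 1 − 0.8 × 0.897/0.88 = 18.5%.

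**Step 5: where the overstatement falls.** For the shared baseline at p = 10%, the relative overstatement is about 25-37% at 0.3 µg and 4-5% at 7 µg. In points it is 2.5, 3.8 and 1.8 at the three doses (gamma fixed) or 3.8, 3.1 and 2.3 (gamma free). If the response instead subtracts a constant 10% of baseline pain, it is 4.9, 6.0 and 7.2 points (gamma free).

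**Step 6: no drug effect at all.** At p = 10% the apparent effect is 1 − 0.9/0.94 = 4.3% with a shared baseline, 10% when measured from pre-infusion pain, and 0% with a placebo term.

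**The case against.** The strongest objection is that the bias depends on an analysis the plan does not state. A reader might infer that the model must pool saline with pre-infusion scores, or that the trial has no placebo-controlled analysis at all. The documents support neither. The primary outcome's time frame covers only post-infusion scores; on that reading saline is the sole zero-dose level, and step 4 shows no bias for a proportional response. The parameter list also omits a baseline, which any model of pain scores needs, so it may not be complete. Saline is dose 0 of the modelled dose-response and is nowhere excluded. This answers any claim of certain bias, but it does not supply the missing specification: a model of pain over time could equally include the pre-infusion scores.

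Two other strong readings also fail.

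- A reader might conclude that the harm is greatest at the lowest dose. That holds in relative terms only; step 5 shows that in points the worst dose changes with the model.
- A reader might quote a false-positive rate. Simulations with no drug effect and assumed variances passed the 6.6 threshold in 23-24% of trials at p = 10% and 65-77% at p = 20%. A stricter model gave 11-13% and 33-34%. The threshold is borrowed from the covariate rule, and the plan has no drug-effect test to which these rates could apply. They are illustrative only.

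One further objection stands in full. Because saline is only ever the first infusion, a placebo term estimated from it also captures early change from repeated heating. Its equality at the second infusion cannot be checked.

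**Conclusion.** The concern holds as a gap in specification with a conditional bias. What is certain is that the Analytical Plan gives no saline comparison, no placebo-response term, no criterion for an oxytocin effect and no rule for the zero-dose records. The bias ranges from none (post-infusion scores only, proportional response) through part of the common response (shared baseline) to all of it (effect measured from pre-infusion pain). The sizes rest on an assumed placebo response, the plan's own curve with Emax 55%, and a flat effect over the three tests. With no placebo response there is no bias. The plan should be amended because these choices determine what Emax, C50 and gamma mean, and because the data needed are already being collected.

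**What to change.** Add to the Analytical Plan:

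1. **Reference.** Make saline the reference for drug effect. Either include a placebo-response parameter that applies after every infusion, saline included, or use only post-infusion records for the zero-dose level. Emax, C50 and gamma then describe effect beyond saline. State which records define baseline.
2. **Criterion.** Claim an oxytocin effect only if the model with oxytocin improves on the model without it, at a stated threshold. Report each dose-minus-saline difference with a 95% CI.
3. **Model-free check.** Report 0.3 µg against saline, using the mean of the three tests. Both are first infusions and visit order is randomised, so this is the direct placebo comparison. Report 7 against 1.3 µg as a same-position dose contrast, not a placebo contrast.
4. **Limits.** State that saline is always first and 1.3 and 7 µg always second. The placebo term therefore includes early drift from repeated heating, and the 1.3 and 7 µg differences from saline assume that the term is the same at the second infusion.

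The cost is some text, one extra parameter and slightly wider intervals. Visits, infusions and sample size do not change.
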